## STUDY SCHEDULE

Visit	Time	Window	Purpose and Activities
1	Day 0	Baseline	Enroll, consent, baseline data
2	Day 1	before 1m data	Intervention visit 1: health edu
3	Day 3	before 1m data	Intervention visit 2: health edu
4	Day 30	+7 days	1m data collection visit
5	Day 45	before 3m data	Intervention visit 3: self-efficacy
6	Day 60	before 3m data	Intervention visit 4: self-efficacy
7	Day 75	before 3m data	Intervention visit 5: self-efficacy
8	Day 90	±7 days	3m data collection visit
9	Day 105	before 6m data	Intervention check-in 1
10	Day 135	before 6m data	Intervention check-in 2
11	Day 150	before 6m data	Intervention check-in 3
12	Day 165	before 6m data	Intervention check-in 4
13	Day 180	±30 days	6m data collection visit
14	Day 365	±30 days	12m data collection visit
15	Day 366	±7 days	Intervention visit 1: health edu*
16	Day 366	±7 days	Intervention visit 2: health edu*
17	Day 395	±7 days	Intervention visit 3: self-efficacy*
18	Day 410	±7 days	Intervention visit 4: self-efficacy*
19	Day 425	±7 days	Intervention check-in visit 1*
20	Day 440	±7 days	Intervention check-in visit 2*
21	Day 455	±30 days	3m data collection visit*
22	Day 545	±30 days	6m data collection visit*

*\*Study visits including intervention visits occurring in the control community for participants interested in exercising their option to participate in the intervention.*

### 6.1 Screening

Based on the lists we obtain of potentially eligible children, caregivers will be contacted by phone, at which point study staff will describe the study, screen for eligibility, and set up a time to enroll and consent if the caregiver is interested. Families will first be contacted about 1 month before enrollment begins.

#### Screening Visit (Day -30 to -1)

- Confirm eligibility (child ages 1 to 11 years, Yup'ik descent, lives in the study community, has a caregiver age 18 years or older) and interest in participating.
- If screening performed in person, obtain and document consent from potential participant on consent form. Obtain and document assent from children ages 8 to 11 years on assent form.
- If participant is available, collect baseline data (see next section).
- If screening performed by phone, schedule baseline visit, during which time consent and assent will be obtained and baseline data will be collected.
- In case of remote informed consent due to Covid-19 restrictions, send the person a link to a combined consent/assent form in REDCap and conduct informed consent via phone.

## 6.2 Enrollment/Baseline

### Enrollment/Baseline Visit (Visit 1, Day 0)

- Verify inclusion/exclusion criteria.
- Obtain and document consent from participant on study consent form. Obtain and document assent from children ages 8 to 11 years on assent form. If visit conducted remotely, obtain electronic signatures from adult and child.
- Obtain fruit drink survey data, 24-hour food recall and food survey data for each enrolled child, plaque sample from child, hair sample and hair survey from each child participant, and hair sample and hair survey from the primary caregiver in the household (see Appendix for surveys and instructions for self-collection of hair samples).
- If visit conducted remotely, obtain survey data via phone and enter in REDCap and assist participants with collection of hair samples using kit mailed to them. No plaque sample will be collected in case of remote study implementation.
- Provide participants with instructions needed to prepare for Visit 2 (available at home for about 40 minutes, child is present, no anticipated distractions or interruptions).

## 6.3 Intermediate Visits

### Visit 2, Day 1 (before 1m data)

This is the first intervention visit.

- Answer any questions family member has about program.

- Administer the first video health education (about 15 minutes long) (see Manual of Procedures).
- Complete exercises within the video (about 10 minutes long) (see Manual of Procedures).
- Assign first homework assignment (see Manual of Procedures).
- If visit conducted remotely, administer video education and homework via phone or Internet. If visit is in person, use PPE and other precautions consistent with community and UW safety protocols.
- Provide participants with instructions needed to prepare for Visit 3 (available at home for about 30 minutes, have about a gallon of drinking water on hand, child is present, no anticipated distractions or interruptions). In case of remote delivery, send samples of sugar-free water enhancers to the participant by mail.
- Offer exchange of sugar-free drink enhancers for sugared fruit drinks in the home. Family may return the sugared fruit drinks to staff after the visit, arrangements may need to be made to pick them up from the home, or this may need to occur at the next visit.
- CHW completes structured visit form to record participant's compliance with the intervention (e.g., watched the video, children were present, no distractions), intervention components that were delivered, intervention components that were modified or not delivered (along with reasons), follow up items (e.g., get the family a particular flavor sample), and additional notes that will help the CHW deliver subsequent intervention components (see Manual of Procedures).

### **Visit 3, Day 3 (before 1m data)**

This is the second intervention visit.

- Review first homework assignment.
- Administer the second video health education (about 5 minutes long) (see Manual of Procedures).
- Complete exercises within the video including mixing of sugar-free drinks (about 20 minutes long) (see Manual of Procedures). Provide samples of sugar-free water enhancers.
- If visit conducted remotely, administer video education and homework via phone or Internet. If visit is in person, use PPE and other precautions.
- Assign second homework assignment (see Manual of Procedures).
- CHW completes structured visit form (see Manual of Procedures).

## **Visit 4, Day 30 + 7 days**

This is the first data collection visit after the baseline visit (1 month).

- Obtain fruit drink survey data, 24-hour food recall and food survey data for each enrolled child, plaque sample from child, hair sample and hair survey from each child participant, hair sample and hair survey from the primary caregiver in the household, and side effects/adverse events (see Appendix for surveys and instructions for self-collection of hair samples).
- If visit conducted remotely, obtain survey data via phone and enter in REDCap and assist participants with collection of hair samples using kit mailed to them. No plaque sample will be collected in case of remote study implementation.

## **Visit 5, Day 45 (before 3m data)**

This is the third intervention visit.

- Review second homework assignment (see Manual of Procedures).
- Plan for future resistance to behavior change and identify strategies to overcome barriers.
- Assign homework to allow caregivers to document barriers and solutions (see Manual of Procedures).
- Follow up with sugared fruit drink exchange (if applicable and interested).
- Distribute vouchers for sugar-free drinks.
- If visit conducted remotely, administer video education and homework via phone or Internet. If visit is in person, use PPE and other precautions.
- Collect data on side effects/adverse events (see Appendix). CHW completes structured visit form (see Manual of Procedures).

## **Visit 6, Day 60 (before 3m data)**

This is the fourth intervention visit.

- Review homework on barriers and solutions to adoption of sugar-free water enhancers.
- Plan for future resistance to behavior change and identify strategies to overcome barriers.

- If visit conducted remotely, administer homework and plan for overcoming barriers via phone. If visit is in person with Covid-19 risk, use PPE and other precautions.
- Assign homework to track barriers and solutions (see Manual of Procedures).
- Collect data on side effects/adverse events (see Appendix).
- Distribute vouchers for sugar-free drinks.
- Community Health Worker completes structured visit form (see Manual of Procedures).

### **Visit 7, Day 75 (before 3m data)**

This is the fifth intervention visit.

- Review homework on barriers and solutions to adoption of sugar-free water enhancers.
- Plan for future resistance to behavior change and identify strategies to overcome barriers.
- If visit conducted remotely, administer homework and plan for overcoming barriers via phone. If visit is in person, use PPE and other precautions.
- Assign homework for caregivers to continue tracking barriers and solutions.
- Collect data on side effects/adverse events (see Appendix).
- Distribute vouchers for sugar-free drinks.
- CHW completes structured visit form (see Manual of Procedures).

### **Visit 8, Day 90 ± 7 days**

This is the second data collection visit after the baseline visit (3 months).

- Obtain fruit drink survey data, optional 24-hour food recall and food survey data for each enrolled child, plaque sample from children, hair samples and hair survey from each child participant, hair samples and hair surveys from the primary caregiver in the household (or another caregiver if the primary caregiver is not present), and side effects/adverse events for intervention families (see Appendix for surveys and instructions for self-collection of hair samples). Dietary 24 hour food recalls and food survey data may or may not be collected, for all participants, at the discretion of the PI. If visit conducted remotely, obtain survey data via phone and enter in REDCap and assist participants with collection of hair samples using kit mailed to them. No plaque sample will be collected in case of remote study implementation.

### **Visit 9, Day 105 ± 7 days**

This is the first brief check-in visit.

- Check in on families and ask about progress (barriers and solutions), provide encouragement, give vouchers.
- In case of remote implementation, call families on the phone. If in person use PPE and other precautions. Send samples by mail.
- Collect data on side effects/adverse events (see Appendix).

### **Visit 10, Day 135 ± 7 days**

This is the second brief check-in visit.

- Check in on families and ask about progress, provide encouragement, give vouchers.
- In case of remote implementation, call families on the phone. If in person use PPE and other precautions. Send vouchers by mail.
- Collect data on side effects/adverse events (see Appendix).

### **Visit 11, Day 150 ± 7 days**

This is the third brief check-in visit.

- Check in on families and ask about progress, provide encouragement, give vouchers.
- In case of remote implementation, call families on the phone. If in person use PPE and other precautions. Send vouchers by mail.
- Collect data on side effects/adverse events (see Appendix).

### **Visit 12, Day 165 ± 7 days**

This is the fourth brief check-in visit.

- Check in on families and ask about progress, provide encouragement, give vouchers.
- In case of remote implementation, call families on the phone. If in person use PPE and other precautions. Send vouchers by mail.
- Collect data on side effects/adverse events (see Appendix).

### **Visit 13, Day 180 + 30 days**

This is the third data collection visit after the baseline visit (6 months).

- Obtain fruit drink survey data, beverage intake data on the child participants using a validated questionnaire administered to the caregivers, plaque sample from children, hair samples and hair survey from each child participant, hair samples and hair surveys from the primary caregiver in the household (or another caregiver if the primary caregiver is not present), and side effects/adverse events for intervention families (see Appendix for surveys and instructions for self-collection of hair samples). Dietary 24 hour food recalls and food survey data may or may not be collected, for all participants, at the discretion of the PI.
- Conduct semi-structured interviews with caregivers in the intervention arm about their family's consumption of sugared fruit drinks, consumption and availability of sugar-free alternatives, and their experiences throughout the intervention.
- If visit conducted remotely, obtain survey data via phone and enter in REDCap and assist participants with collection of hair samples using kit mailed to them. No plaque sample will be collected in case of remote study implementation.

#### **6.4 Final Study Visit**

##### **Visit 14, Day 365 + 30 days**

This is the fourth data collection visit after the baseline visit (12 months).

- Obtain fruit drink survey data, beverage intake data on the child participants using a validated questionnaire administered to the caregivers, plaque sample from children, hair samples and hair survey from each child participant, hair samples and hair surveys from the primary caregiver in the household (or another caregiver if the primary caregiver is not present), and side effects/adverse events from families in the intervention arm (see Appendix for surveys and instructions for self-collection of hair samples). Dietary 24 hour food recalls and food survey data may or may not be collected, for all participants, at the discretion of the PI. The fruit drink surveys may be completed by participants using a paper version of the survey form adapted from the versions from the REDCap database.
- If visit conducted remotely, obtain survey data via phone and enter in REDCap and assist participants with collection of hair samples using kit mailed to them. Conduct the post-study interview and provide final instructions by phone. No plaque sample will be collected in case of remote study implementation.

- Conduct semi-structured interviews with caregivers about their family's consumption of sugared fruit drinks, consumption and availability of sugar-free alternatives, and their experiences throughout the intervention; along with post-study feedback on how the program went, any perceived changes in sugared fruit drink behaviors, difficulties and ways to improve the program (see Appendix and Manual of Procedures). Some of the questions from the semi-structured interviews may be answered by participants using a paper based survey, prior to the in-person interview.
- Provide final instructions to participant (e.g., side effects, adverse events, how to contact with questions) (see Manual of Procedures).
- Obtain consent and assent for families and children in the control arm who are interested in participating in the second phase of the study for the modified control community intervention.

## **6.5 Additional Study Visits for Control Arm**

### **Visit 15, Day 366 ± 7 days**

This is the first control community intervention visit.

- The components of this intervention visit will be the same as with Communities A and B (see visit 2 above).
- The control community intervention may be delivered by UW Study staff, or a CHW, in person.

### **Visit 16, Day 366 ± 7 days**

This is the second control community intervention visit.

- The components of this intervention visit will be the same as with Communities A and B (see visit 3 above).
- The control community intervention may be delivered by UW Study staff, or a CHW, in person.

### **Visit 17, Day 395 ± 7 days**

This is the third control community intervention visit.

- The components of this intervention visit will be the same as with Communities A and B (see visit 5 above).

- The control community intervention may be delivered by UW Study staff, or a CHW, in person or by Zoom, phone, or text message.

### **Visit 18, Day 410 ± 7 days**

This is the fourth control community intervention visit.

- The components of this intervention visit will be the same as with Communities A and B (see visit 5 above).
- The control community intervention may be delivered by UW Study staff, or a CHW, in person or by Zoom, phone, or text message.

### **Visit 19, Day 425 ± 7 days**

This is the first brief check-in visit.

- Check in on families and ask about progress (barriers and solutions), provide encouragement.
- In case of remote implementation by UW study staff, families will be called on the phone. If a CHW is available, the check-in visit may be completed in person or by Zoom, phone, or text message.

### **Visit 20, Day 440 ± 7 days**

This is the second brief check-in visit.

- Check in on families and ask about progress (barriers and solutions), provide encouragement.
- In case of remote implementation by UW study staff, families will be called on the phone. If a CHW is available, the check-in visit may be completed in person or by Zoom, phone, or text message.

### **Visit 21, Day 455 +/- 30 days**

This is the first data collection visit after the 12-month data collection from the main study (3m data collection visit for controls).

- Obtain fruit drink survey data, beverage intake data on the child participants using a validated questionnaire administered to the caregivers, plaque sample

from children, hair samples and hair survey from each child participant, hair samples and hair surveys from the primary caregiver in the household (or another caregiver if the primary caregiver is not present), and side effects/adverse events from families in the intervention arm (see Appendix for surveys and instructions for self-collection of hair samples). Dietary 24 hour food recalls and food survey data may or may not be collected, for all participants, at the discretion of the PI.

- Conduct semi-structured interviews with caregivers about their family's consumption of sugared fruit drinks, consumption and availability of sugar-free alternatives, and their experiences throughout the intervention; along with post-study feedback on how the program went, any perceived changes in sugared fruit drink behaviors, difficulties and ways to improve the program (see Appendix and Manual of Procedures).

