There are 2 arms: an intervention arm and a control arm. 136 children in Communities A and B will be assigned to the intervention arm (in-person video-based health education led by a Community Health Worker, self-efficacy coaching, brief "check-ins", access to stores that sell the target sugar-free water enhancers). In case of Covid-19 restrictions the health education and self-efficacy coaching may be delivered via phone or Internet video and the check-ins via phone, video call, or in-person outside the home. There will be a total of 5 visits and 4 brief "check-ins" (total face time of 2-3 hours). This visit frequency was determined as acceptable by community members in terms of being sufficient time to educate caregivers and motivate behavior change without overburdening families. Indigenous Community Health Workers who are from and live in the study communities will deliver all intervention components to maximize cultural saliency.

56 children in Community C will be assigned to the delayed treatment control arm. Children in the control arm will have the opportunity to receive similar intervention components after the study ends, that incorporates learned lessons from the

intervention to improve content and delivery. If Covid-19 continues to result in restrictions at the end of the study Community C participants may also receive virtual visits by phone or Internet video. This will involve CHW or UW study staff-delivered health education, self-efficacy training, and check-ins. We will provide families with an equivalent number of sugar-free water enhancers distributed during the second health education visit for the intervention communities, based on household size. We will work with stores to start selling sugar-free water enhancers from the start of the control community intervention throughout the 6-months. We will also inform stores that there may be increased demand for these sugar-free water enhancers and provide them with ordering information. The control community intervention however, will last only 3 months, one-half of the time over which families in Communities A and B will have received the intervention. We will evaluate outcomes for control families for as long as the budget will allow.

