## STUDY PROCEDURES/EVALUATIONS

### 7.1 Study Procedures/Evaluations

Study staff and CHWs will work with store staff in the 2 intervention communities to make sure the sugar-free water enhancers are available throughout the study period. This will involve the CHW visiting the stores weekly to monitor availability, to work with stores to order more if needed, to check with families to make sure they are not experiencing any difficulties finding or buying the drinks, and to problem solve with store owners to address any unanticipated barriers to families finding or buying the drinks. For all in-person study procedures, including store visits, the CHWs will use PPE and other precautions. UW study staff will also work with the store in the control community to make sure the sugar-free water enhancers are available throughout the control community intervention.

**Data Collection Frequency.** In all study communities, there will be 5 data collection visits (baseline, 1 month, 3 months, 6 months, and 12 months) which will take place separately from the intervention visits. In the control community, there will be 2 additional data collection visits (3-months and 6-months) after the initial 12-month study period.

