The **plaque sample** will be collected and banked at the UW for future analyses to determine the effects of the intervention on bacteria in the mouth. The **hair sample** will be used to measure added sugar intake using a validated biomarker (Nash et al. 2013). The hair sample is accompanied by a short **hair survey** regarding hair condition (e.g., bleached, dyed, etc.). The plaque sample will not be collected in case of remote study implementation.

A **side effects and adverse events form** will be used to record data on potential and other events that could come from excess intake of the sugar-free water enhancers, as a measure of safety, and to allow our team to intervene as needed to minimize any potential side effects associated with the intervention. This form will only be collected from intervention families.

At subsequent data collection visits, the same information will be collected except for demographic data, 24-hour food recalls, and food surveys. The 6-month and final visit (12-month) will include **semi-structured interviews** with caregivers to qualitatively assess perceived changes in sugared fruit drink consumption, behavior changes, obtain feedback about the program, benefits and drawbacks, and ways to improve the program. Incentives will be given at each data collection visit. For the 12-month data collection visit (and control community intervention data collection visits), some of the questions from the semi-structured interviews may be answered by participants using a paper-based survey, prior to the in-person interview.

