At each study visit, a CHW or study staff will ask the caregiver about any side effects experienced from the sugar-free water enhancers and will work with the caregiver to assess severity, source, and remedies. If the symptoms or side effects have persisted for more than 48 hours, the CHW will contact the Research Coordinator and Study PI to report the problem to a local health aide. The medical health aides are individuals who live in the communities and are the front-line primary medical care providers in the study communities. They will be asked to follow up with the family and determine the best course of treatment (e.g., monitor, hydration therapy, other). Between study visits, if a caregiver suspects that their child is experiencing side effects associated with the sugar-free water enhancers, they will be asked to contact the CHW. The CHW will then contact the Research Coordinator and Study PI. The Study PI will work with the caregiver and medical health aide to identify the possible cause of the side effects or the relationship of the adverse events to the study intervention.

Side effects/adverse events will be classified as mild, moderate, or severe (see Manual of Procedures). If the side effects are mild or moderate, the child's sugar-free water enhancer intake will be reduced, and the child's side effects will be monitored over the next 48 hours to see if the symptoms resolve. If symptoms are severe or continue past 48 hours, the caregiver will be asked to stop giving the child the sugar-free drinks and to visit the local health aide. If the child's symptoms resolve, caregivers can elect to continue giving their child the sugar-free drinks under close supervision. If the same

symptoms or side effects return a second time, the child's participation in the intervention will be terminated. The child and caregiver will be encouraged to still be involved in all subsequent data collection visits.

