## **8.5 Time Period and Frequency for Event Assessment and Follow-Up**

The PI will record all events with start dates occurring any time after informed consent is obtained until 7 (for non-serious AEs) or 30 days (for SAEs) after the last day of study participation. At each study visit, the Community Health Worker or Study Staff will inquire about the occurrence of AE/SAEs since the last visit. Events will be followed for outcome information until resolution or stabilization.

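### Visits 21 and 22 name the wrong families for side-effect collection, and the control-phase safety text contradicts the general rules in 8.1 and 8.5

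*Combined protocol and SAP*

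**What the plan says.** **Who attends.** The footnote to the Study Schedule table describes visits 15 to 22 as "Study visits including intervention visits occurring in the control community for participants interested in exercising their option to participate in the intervention". Section 7.1 agrees: "In the control community, there will be 2 additional data collection visits (3-months and 6-months) after the initial 12-month study period".

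**Exposure.** Under Study Design, the control community is to receive product in this phase: "We will provide families with an equivalent number of sugar-free water enhancers distributed during the second health education visit for the intervention communities". The local store is also to stock it.

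**Text that points away from these families.** At visits 21 and 22 (section 6.5), the list of data to obtain includes "side effects/adverse events from families in the intervention arm". Section 7.1 says of the side-effects form: "This form will only be collected from intervention families". The entries for control check-ins 19 and 20 mention progress and encouragement but not side effects. The four check-ins in Communities A and B (visits 9 to 12, section 6.3) each include a side-effect item.

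**Text that points towards them.** Section 8.1: "At each study visit, a CHW or study staff will ask the caregiver about any side effects experienced from the sugar-free water enhancers". Section 8.5: "At each study visit, the Community Health Worker or Study Staff will inquire about the occurrence of AE/SAEs since the last visit". Neither is limited to an arm. Control visits 17 and 18 take their components from visit 5, which includes side-effect collection. The control-visit table in Appendix A marks the side-effects row twice.

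**The concern.** Children in the control community first receive the sweetened products through the study after month 12. From then on they are the exposed group, and the protocol's safety questions exist to detect effects of that exposure. At the two data visits designed for them, the written procedure directs the questions to families who are elsewhere. The phrase is the same as at visit 14, which both arms attend and where limiting the item to intervention families makes sense. It appears to have been carried over.

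What is at stake is complete and uniform safety data in the delayed phase. Field staff work mainly from visit descriptions and forms. If those disagree with the general safety section, whether a family is asked may depend on which page the staff member follows. Section 8.8 calls for an ad hoc review when more than 20% of children have symptoms thought to be linked to the products. Missed events can only lower the number of children seen to have symptoms.

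**Working it through.** The plan gives no figure to reproduce. The check sets the passages side by side and reads the timing from the Study Schedule table.

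**Step 1: what each visit description provides for the families who attend.**

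- Visits 15 and 16 (Day 366): components of visits 2 and 3, neither of which lists side effects. Communities A and B are treated the same way at this stage.
- Visit 17 (Day 395): components of visit 5, so side effects are collected.
- Visit 18 (Day 410): components of visit 5, so side effects are collected.
- Visits 19 and 20 (Days 425 and 440): no side-effect item.
- Visits 21 and 22 (Days 455 and 545): side-effect item present, but directed at the intervention arm.

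From about one month after first exposure, the visit text provides collection at 2 of 6 control visits (17 and 18 out of 17 to 22). For Communities A and B, every visit from Day 30 on lists it: visits 4 to 14, or 11 of 11.

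**Step 2: length of the gap if the visit text is followed literally.**

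- Last visit with the item: Day 410. Last scheduled visit: Day 545.
- Gap = 545 − 410 = **135 days**.
- Using the windows (±7 days at visit 18, ±30 days at visit 22): shortest (545 − 30) − (410 + 7) = 515 − 417 = 98 days; longest (545 + 30) − (410 − 7) = 575 − 403 = 172 days.

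**Step 3: number of children.** The planned control enrolment is 56. This is a ceiling, because the delayed intervention is optional and some children will have left the study. The protocol gives no expected uptake.

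**Step 4: compare the sources for the same children.**

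- Visit descriptions: collection at visits 17 and 18 only.
- Appendix A, control-visit table: two marks, in the same positions as the hair and plaque marks, so apparently the two data visits. Column alignment in the text available is uncertain, and the exact column is not relied on here.
- Sections 8.1 and 8.5: every study visit, so 6 of 6 from visit 17 on.
- Section 7.1: the form is for intervention families only.

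These cannot all be followed at once.

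**Step 5: can the wording be read so that it works?** One could say that control families become intervention families once they start the delayed programme. The protocol never says this. Study Design and section 4.4 define the intervention arm as Communities A and B, and section 13.1 still refers to the treated families of the delayed phase as belonging to the control community.

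**The case against.** The strongest reply is that a reader might infer that these children's events go uncollected as written, and the documents do not support that. Sections 8.1 and 8.5 require inquiry at each study visit without regard to arm. Section 8.5 has the investigator record all events from consent until 7 days (30 days for serious events) after the last day of participation. Section 8.1 asks caregivers to report suspected side effects between visits. Visits 17 and 18 bring in the visit 5 item. Nothing shows a decision to leave these children unmonitored. All of this stands, and it limits the point to a contradiction between passages.

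Three other strong readings also fail:

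- **That several places jointly exclude these children.** Silence at visits 19 and 20 is not exclusion when a general rule covers every visit. The Appendix J list that stops at study visit 12 is a list of home visits. It also omits visits 4, 8, 13 and 14, where side effects are expressly collected, so absence from it proves nothing.
- **That the gap covers the whole delayed phase, about 180 days (Day 366 to 545).** This ignores visits 17 and 18.
- **That control-phase events would not count toward the 20% trigger.** Section 8.8 does not restrict by arm, visit or form.

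What survives is that a general rule does not cure a specific instruction that contradicts it. The visit text names particular families and 7.1 restricts the form on its face. The between-visit route is also weaker here: caregivers are told to contact the Community Health Worker, and sections 5.2 and 5.3 allow for the control community not having one.

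**Conclusion.** The point holds as an internal inconsistency with a practical safety consequence. The phrase at visits 21 and 22 and the restriction in 7.1 conflict with 8.1, 8.5, the cross-reference from visits 17 and 18, and Appendix A. Check-ins 19 and 20 lack an item that the matching check-ins in Communities A and B have.

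The size is conditional. If staff follow the visit descriptions, up to 56 newly exposed children have no scheduled side-effect questions from Day 410 to Day 545, 135 days on nominal dates. If staff follow 8.1 and 8.5, there is no gap. The documents do not say which takes precedence. The figures assume that all 56 planned children enter the delayed phase and that visits fall on their nominal days.

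The primary comparison at 6 months is not affected. What could be incomplete is the safety record of the delayed phase, including the information available to the review in 8.8. The correction should be made, because the error sits in a stated collection procedure and costs little to remove.

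**What to change.** Reconcile the visit-level text with 8.1 and 8.5:

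1. At visits 21 and 22, replace the phrase with wording that names the families receiving the control community intervention.
2. In 7.1, widen the restriction so that the form covers all families receiving the products, in either phase.
3. At visits 19 and 20, add the side-effect item already used at visits 9 to 12.
4. Confirm that the side-effects row of the Appendix A control-visit table agrees with the result.
5. As a minor form change, add the control intervention visits and check-ins (15 to 20) to the Appendix J visit list.

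The cost is a protocol wording amendment and extra options on one form. No visits are added and no rule for managing side effects changes. If the delayed phase has already run, the report should state at which control visits families were actually asked.
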